7.1.2.7 PK/Pharmacodynamics Assessment

Blood samples for plasma PK and pharmacodynamics assessment will be collected predose (10-30 minutes before L-NMMA infusion) on Days 1, 2, and 5 of Cycles 1 and 2. One 5-mL

sample will be collected for PK assessment and one 5-mL sample will be collected for pharmacodynamics assessment. **NOTE:** For PK/pharmacodynamics assessment, subjects should be fasted (nothing to eat or drink except water) for 12 hours prior to each collection time point. Subjects should also keep a food diary the week before and the week of the L-NMMA infusion during Cycles 1 and 2.

7.1.2.8 Blood Sample Collection, Storage, and Use for Future Research

Blood samples will be collected for future research at baseline, after Cycle 2 of L-NMMA and pembrolizumab, and 3 months after the last dose of trial treatment. Blood (20–30 cc) will be collected into standard vacutainer tubes and processed for plasma and viable cryopreserved peripheral blood mononuclear cells for future analyses. The samples will be stored at the Houston Methodist Research Institute Biorepository Core.

7.1.3 Laboratory Procedures/Assessments

7.1.3.1 Laboratory Tests

Details regarding specific laboratory procedures/assessments to be performed in this trial are provided below.

Laboratory Safety Evaluations (Hematology, Chemistry, and Urinalysis):

Coagulation parameters (INR/PT/aPTT) will be tested at screening. Hepatitis panel and HIV testing will be performed at screening. Thyroid-stimulating hormone, free thyroxine, and total triiodothyronine testing and urinalysis (blood, glucose, protein, specific gravity) will be performed at baseline and when clinically indicated. A blood sample for complete blood count with platelet count and differential white blood cell count will be obtained at screening/baseline, before every cycle of L-NMMA and pembrolizumab, at EOT, and when clinically indicated. A blood sample for clinical chemistry panel (glucose, albumin, sodium, potassium, carbon dioxide, calcium, chloride, blood urea nitrogen, creatinine, total protein, total bilirubin, alkaline phosphatase, ALT, and AST) and evaluation of magnesium, uric acid, and lactate dehydrogenase will be obtained at screening/baseline, before every cycle of L-NMMA and pembrolizumab, at EOT, and when clinically indicated. For subjects with cHL, sedimentation rate testing will be performed at baseline and Cycles 2, 4, and 6 of L-NMMA and pembrolizumab. For women of childbearing potential, the results of a serum β -hCG pregnancy test must be negative at screening. If the screening serum β -hCG pregnancy test is performed more than 7 days before the first dose of trial treatment, it must be repeated at baseline, with results known to be negative prior to the administration of the first treatment dose. β -hCG pregnancy testing is to be repeated when clinically indicated. Laboratory tests may be done more frequently if medically indicated.

Laboratory tests for hematology, chemistry, urinalysis, and others are specified in Table 7.

Table 7. Laboratory Tests

Hematology	Chemistry	Urinalysis	Other
Hemoglobin	Albumin	Blood	Serum β -hCG†
Platelet count	Alkaline phosphatase	Glucose	PT (INR)
White blood cell count (total and differential)	ALT	Protein	aPTT
ANC	AST	Specific gravity	Total triiodothyronine
Sedimentation rate*	Lactate dehydrogenase	Microscopic exam (If abnormal results are noted)	Free thyroxine
	Carbon dioxide		Thyroid-stimulating hormone
	Creatinine		Hepatitis panel
	Uric acid		HIV test
	Calcium		
	Chloride		
	Glucose		
	Potassium		
	Sodium		
	Magnesium		
	Total bilirubin		
	Total protein		
	Blood urea nitrogen		
†Perform on women of childbearing potential only.			
*Perform on subjects with classical Hodgkin lymphoma only.			

7.1.4 Continuation of Pembrolizumab Treatment

Subjects without disease progression after 6 cycles of L-NMMA and pembrolizumab will continue pembrolizumab until disease progression or unacceptable AEs. CT scans of the chest, abdomen, and pelvis and/or other sites as appropriate (e.g., head and neck, upper extremities, lower extremities) will be performed every 3 cycles of pembrolizumab and/or at the discretion of the treating physician. For subjects with previously treated stable brain metastases, brain CT or MRI will be performed every 2 months (± 7 days) as per standard of care. Blood samples for CBC with platelet count and differential WBC count, clinical chemistry panel (glucose, albumin, sodium, potassium, carbon dioxide, calcium, chloride, BUN, creatinine, total protein, total bilirubin, alkaline phosphatase, ALT, and AST), and evaluation of magnesium, uric acid, and LDH will be obtained at every cycle of pembrolizumab. For subjects with cHL, sedimentation rate testing will be performed at every other cycle.

7.1.5 Other Procedures

7.1.5.1 Withdrawal/Discontinuation

When a subject discontinues/withdraws prior to trial completion, all applicable activities scheduled for the final trial visit should be performed at the time of discontinuation. Any AEs which are present at the time of discontinuation/withdrawal should be followed in accordance with the safety requirements outlined in Section 7.2 — Assessing and Recording Adverse Events.

7.1.5.2 Visit Requirements

Visit requirements are outlined in Section 6.0 — Trial Flow Chart. Specific procedure-related details are provided above in Section 7.0 — Trial Procedures.

7.1.5.2.1 Post-Treatment Visits

7.1.5.2.1.1 Safety Follow-Up Visit

The mandatory safety follow-up visit should be conducted approximately 30 days after the last dose of trial treatment or before the initiation of a new anticancer treatment, whichever comes first. All AEs that occur prior to the safety follow-up visit should be recorded. Subjects with an AE of > Grade 1 will be followed until the resolution of the AE to Grade 0–1 or the beginning of a new antineoplastic therapy, whichever occurs first. SAEs that occur within 90 days of EOT or before initiation of a new anticancer treatment should also be followed and recorded.

7.1.5.2.1.2 Survival Follow-Up

Patients who continue to receive pembrolizumab will be followed up for survival status 30 days after the last dose of pembrolizumab.

7.2 Assessing and Recording AEs

An AE is defined as any untoward medical occurrence in a patient or clinical investigation subject administered a pharmaceutical product and which does not necessarily have to have a causal relationship with this treatment. An AE can, therefore, be any unfavorable and unintended sign (e.g., abnormal laboratory finding), symptom, or disease temporally associated with the use of a medicinal product or protocol-specified procedure, whether or not considered related to the medicinal product or protocol-specified procedure. Any worsening (i.e., any clinically significant adverse change in frequency and/or intensity) of a preexisting condition that is temporally associated with the trial treatment is also an AE. Progression of the cancer under study is not considered an AE.

From the time of informed consent signing through 30 days following cessation of treatment, all AEs must be reported by the investigator. AE reporting will be performed according to 21 CFR 312.32. AEs will be recorded at each examination on the Adverse Event CRFs. AEs (including lab abnormalities that constitute AEs) should be described using a diagnosis whenever possible, rather than individual underlying signs and symptoms. When a clear diagnosis cannot be identified, each sign or symptom should be reported as a separate AE. Conditions that were already present at the time of informed consent should be recorded in the Medical History page of the subject's CRF. The reporting timeframe for AEs meeting any serious criteria is described in section 7.2.3.1. The investigator will make every attempt to follow all subjects with non-SAEs for outcome.

AEs will not be collected for subjects during the prescreening period as long as that subject has not undergone any protocol-specified procedure or intervention. If the subject requires a

blood draw, fresh tumor biopsy etc., the subject is first required to provide consent to the main study and AEs will be captured according to guidelines for standard AE reporting.

The occurrence of AEs should be sought by non-directive questioning of the subject at each study visit. AEs may also be detected when they are volunteered by the subject during or between visits or through physical examination, laboratory test, or other assessments. As far as possible, each AE should be evaluated to determine:

1. Severity grade (CTCAE Grade 1–4)
2. Duration (start and end dates or if continuing at the safety follow-up visit)
3. Relationship to the study treatment (reasonable possibility that AE is related: no, yes)
4. Action taken with respect to trial treatment (none, dose adjusted, temporarily interrupted, permanently discontinued, hospitalized, unknown, not applicable)
5. Whether medication or therapy was given (no concomitant medication/non-drug therapy, concomitant medication/non-drug therapy)
6. Outcome (not recovered/not resolved, recovered/resolved, recovering/resolving, recovered/resolved with sequelae, fatal, unknown)
7. Whether it is serious, where a SAE is defined as in Section 7.2.3.1.

All AEs should be treated appropriately. Such treatment may include changes in trial treatment including possible interruption or discontinuation, starting or stopping concomitant treatments, changes in the frequency or nature of assessments, hospitalization, or any other medically required intervention. Once an AE is detected, it should be followed until its resolution, and assessment should be made at each visit (or more frequently, if necessary) of any changes in severity, the suspected relationship to the trial treatment, the interventions required to treat it, and the outcome.

7.2.2 Reporting of Pregnancy and Lactation

Although pregnancy and lactation are not considered AEs, it is the responsibility of investigators or their designees to report any pregnancy or lactation in a subject (spontaneously reported to them) that occurs during the trial.

Pregnancies and lactations that occur from the time of informed consent signing through 120 days following cessation of treatment or 30 days following cessation of treatment if the subject initiates new anticancer therapy, whichever is earlier, must be reported by the investigator. All reported pregnancies must be followed to the completion/termination of the pregnancy. Pregnancy outcomes of spontaneous abortion, missed abortion, benign hydatidiform mole, blighted ovum, fetal death, intrauterine death, miscarriage, and stillbirth must be reported as serious events (Important Medical Events). If the pregnancy continues to term, the outcome (health of infant) must also be reported. Such events must be reported within 24 hours to the Sponsor ([contact]; [contact]).

7.2.3 Immediate Reporting of AEs

7.2.3.1 SAEs

A SAE is any untoward medical occurrence that at any dose:

- Results in death;
- Is life threatening;
- Results in persistent or significant disability/incapacity;
- Results in or prolongs an existing inpatient hospitalization, unless hospitalization is for:
 - routine treatment or monitoring of the studied indication and not associated with any deterioration in condition
 - elective or preplanned treatment for a preexisting condition that is unrelated to the indication under study and has not worsened since the start of trial treatment
 - treatment on an emergency outpatient basis for an event not fulfilling any of the definitions of a SAE given above and not resulting in hospital admission
 - social reasons and respite care in the absence of any deterioration in the subject's general condition;
- Is a congenital anomaly/birth defect;
- Is another important medical event. This refers to an AE that may not result in death, be immediately life threatening, or require hospitalization, but may be considered serious when, based on appropriate medical judgment, may jeopardize the subject, require medical or surgical intervention to prevent one of the outcomes listed above, or involves suspected transmission via a medicinal product of an infectious agent.

From the time of informed consent form signing through 90 days following cessation of treatment or 30 days following cessation of treatment if the subject initiates new anticancer therapy, whichever is earlier, any SAE or follow up to a SAE, including death due to any cause other than progression of the cancer under study, whether or not related to the trial treatment, must be reported within 24 hours to the Sponsor ([contact]; [contact]).

Additionally, any SAE considered by an investigator who is a qualified physician to be related to the trial treatment that is brought to the attention of the investigator at any time following consent through the end of the specified safety follow-up period specified in the paragraph above or at any time outside of the time period specified in the previous paragraph also must be reported immediately to the Sponsor.

All subjects with SAEs must be followed up for outcome.

8.0 STATISTICAL CONSIDERATIONS

This is a Phase Ib trial investigating the use of L-NMMA in combination with pembrolizumab in subjects with melanoma, NSCLC, HNSCC, cHL, urothelial carcinoma, cervical cancer, esophageal cancer, gastric cancer, hepatocellular carcinoma, merkel cell carcinoma, primary mediastinal large B-cell lymphoma, renal cell carcinoma, small cell lung cancer, MSI-H/dMMR cancer or for the treatment of adult patients with unresectable or metastatic tumor

mutational burden-high (TMB-H) [≥ 10 mutations/megabase (mut/Mb)] solid tumors. The study is designed to determine the DLTs and MTD of the L-NMMA plus pembrolizumab combination. DLT will be defined as any treatment-related death or any \geq Grade 3 AE (NCI CTCAE v4.03) unless there is clear alternative evidence that the AE was not caused by the trial treatment. DLT will also include any AE during Cycle 1 that delays administration of Cycle 2 by more than 7 days:

- Grade 4 neutropenia ($ANC < 500/mm^3$) lasting ≥ 7 days
- Grade 3 febrile neutropenia lasting > 24 hours (single temperature of $> 38.3^\circ C$ or a sustained temperature of $> 38^\circ C$ for > 1 hour (non-axillary) with $ANC < 1000/mm^3$)
- Grade 4 febrile neutropenia of any duration
- Grade 4 thrombocytopenia (platelets $< 25,000/mm^3$) or Grade 3 thrombocytopenia with significant bleeding
- Hematological toxicities can be managed for a period that will not exceed more than 7 days. In the event that the hematological toxicity persists for more than the allowed time, it will be considered a DLT
- Grade 3–4 elevation in ALT or AST associated with a Grade 2 elevation in bilirubin that is at least possibly related to study drug (Hy's Law)
- Any \geq Grade 3 electrolyte abnormality considered clinically significant or which lasts ≥ 72 hours
- Grade 3 infusion-related reactions that recur despite appropriate medical management
- Any other treatment-related \geq Grade 3 non-hematological AE except hyperlipidemia in subjects not receiving maximum medical management or electrolyte abnormalities that may be managed with supplements

The study will utilize the sequential CRM for two-dimensional dose finding method of Yuan and Yin,⁶⁷ a method based entirely on a Bayesian decision framework. The trial is designed to investigate the combination at one dose level of pembrolizumab (200 mg IV Q3W) and 3 dose levels of L-NMMA (12.5, 15.0, and 20.0 mg/kg). The starting dose will be pembrolizumab at 200 mg IV Q3W and L-NMMA at 15.0 mg/kg. The trial will be comprised of 12 subjects and will utilize a standard Bayesian model averaging CRM approach to determine the appropriate dose of L-NMMA. A cohort size of 2 will be used.

The study was designed and will be conducted using Bayesian model averaging CRM software developed by the Biostatistics Department of the University of Texas M. D. Anderson Cancer Center (<https://biostatistics.mdanderson.org/SoftwareDownload/>).^{68,69} The software assumes the probability of toxicity at dose i (π_i) is modeled as $\pi_i = p_i \times \exp(\alpha)$ where p_i is a constant and α is distributed a priori as a normal random variable with mean 0 and variance 2. The software requires the investigator to specify the prior median probability of toxicity at each of the 3 doses of L-NMMA under consideration (s_i , $i = 1, 2, 3$). The CRM model assumes that toxicity is a monotonic increasing function with dose and thus, the s_i values may not decrease as i increases. The values p_i in the probability model are selected so that $E[p_i \times \exp(\alpha)] = s_i$. After the first cohort, each successive cohort is given the dose whose posterior probability of toxicity given the data collected thus far is closest to the target toxicity (the software does not allow an untried dose to be skipped). Thus as information accumulates, the model is continually updated *posteriorly* and decisions are made on the *posterior* distribution. As a result, no data is lost and

there is the assurance that the decision to increase or decrease the dose level is consistently reassessed as more information becomes available. For a dose level to be chosen as the MTD, at least 6 subjects must have received said dose.

Table 8. L-NMMA Dose Escalation

Dose Level	L-NMMA (mg/kg)
-1	12.5
0	15.0
1	20.0

The target toxicity probability will be 0.25 to 0.30 and a maximum of 12 subjects will be treated. The first cohort of subjects will be treated at dose level 0. As an extra measure of safety, the trial will be stopped early if the lowest dose level is unacceptably toxic, formally if

$$P_r\{p_{-1} \times e^{\alpha} > 0.25 | data\} > 0.80.$$

The Bayesian model averaging CRM will be implemented using the following three toxicity probability sets: 1) $(p_{-1}, p_0, p_1) = (0.05, 0.10, 0.15)$; 2) $(p_{-1}, p_0, p_1) = (0.15, 0.275, 0.40)$; and 3) $(p_{-1}, p_0, p_1) = (0.40, 0.50, 0.60)$. Operating characteristics of the design under five dose-toxicity scenarios are tabulated below.

Table 9. Phase Ib Design Operating Characteristics (optimal decisions are given in boldface type)

Scenario	Study Parameter	Dose Level			None
		-1	0	1	
1	Prob[toxicity]	0.05	0.10	0.15	0.03
	% Selected	0.03	0.18	0.77	
	# treated	1.0	3.3	7.5	
2	Prob[toxicity]	0.10	0.175	0.25	0.10
	% Selected	0.13	0.32	0.46	
	# treated	2.1	3.9	5.2	

3	Prob[toxicity]	0.15	0.25	0.35	0.20
	% Selected	0.24	0.34	0.22	
	# treated	2.9	4.0	3.5	
4	Prob[toxicity]	0.20	0.30	0.40	0.29
	% Selected	0.30	0.27	0.13	
	# treated	3.2	3.8	2.7	
5	Prob[toxicity]	0.40	0.50	0.60	0.75
	% Selected	0.17	0.05	0.01	
	# treated	2.8	2.6	0.8	

Under Scenario 5 in which all dose levels are too toxic, the estimated probability of finding no acceptable dose is 0.75 with the trial design choosing a dose with 40% toxicity 17% of the time. Scenario 1 represents a setting in which none of the doses is too toxic. For this scenario, the design would chose the highest dose as the MTD 77% of the time.

Data management. CRFs will be designed and utilized to capture all patient data. An electronic database will be designed to store patient CRFs. Data quality control will be performed regularly by the research coordinator to ensure timely, accurate, and complete patient data collection as well as protocol compliance. Queries will be generated and resolved prior to the generation of interim and final summary reports.

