3.0 ENDPOINTS

3.1 Primary Endpoint

- The primary endpoint will be the identification of the MTD of the L-NMMA and pembrolizumab combination. DLT will be defined as any treatment-related death or any \geq Grade 3 AE (NCI CTCAE v4.03) unless there is clear alternative evidence that the AE was not caused by the trial treatment (see Section 8.0 — Statistical Considerations for a detailed list of DLTs). The DLT assessment window will be defined as the duration required to complete one full cycle of treatment with the L-NMMA and pembrolizumab combination. If treatment is delayed, the timelines for dose escalation and MTD determinations will be adjusted to allow for the completion of the DLT assessment window. Subjects will be considered evaluable for the purpose of establishing dose escalation decisions and the MTD if they satisfy one of the following criteria: receive at least one complete cycle of the L-NMMA and pembrolizumab combination and complete trial assessments without a DLT within the DLT assessment window or experience a DLT within the DLT assessment window and are withdrawn from the trial.

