5.2.1.2 Dose Modification

Pembrolizumab:

AEs (both non-serious and serious) associated with pembrolizumab exposure may represent an immunologic etiology. These AEs may occur shortly after the first dose or several months after the last treatment dose.

Withhold pembrolizumab for any of the following:

- Grade 2 pneumonitis

- Grade 2 or 3 colitis
- Grade 3 or 4 endocrinopathies
- Grade 4 hematological toxicity in subjects with cHL
- Grade 2 nephritis
- AST or ALT > 3 and up to 5 X ULN or total bilirubin > 1.5 and up to 3 X ULN
- Any other severe or Grade 3 treatment-related AE

Resume pembrolizumab in subjects whose AEs recover to Grade 0–1.

Permanently discontinue pembrolizumab for any of the following:

- Any life-threatening AE (excluding endocrinopathies controlled with hormone replacement therapy or hematological toxicity in subjects with cHL)
- Grade 3 or 4 pneumonitis or recurrent pneumonitis of Grade 2 severity
- Grade 3 or 4 nephritis
- AST or ALT > 5 X ULN or total bilirubin > 3 X ULN
 - For subjects with liver metastasis who begin treatment with Grade 2 ALT or AST, if ALT or AST increases by $\geq 50\%$ relative to baseline and lasts for at least 1 week
- Grade 3 or 4 infusion-related reactions
- Inability to reduce corticosteroid dose to 10 mg or less of prednisone or equivalent per day within 12 weeks
- Persistent Grade 2 or 3 AEs (excluding endocrinopathies controlled with hormone replacement therapy) that do not recover to Grade 0–1 within 12 weeks after the last dose of pembrolizumab
- Any severe or Grade 3 treatment-related AE that recurs

L-NMMA:

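### Sections 3.1 and 8.0 give two DLT rules that disagree on some hematological, electrolyte and hyperlipidemia events, and nothing says which one governs the dose decisions

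*Combined protocol and SAP*

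**What the plan says.** **General rule.** Section 8.0 states: "DLT will be defined as any treatment-related death or any" AE of Grade 3 or higher, "unless there is clear alternative evidence that the AE was not caused by the trial treatment". Section 3.1 (Primary Endpoint) repeats this and adds "see Section 8.0 — Statistical Considerations for a detailed list of DLTs".

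**List.** Section 8.0 continues: "DLT will also include any AE during Cycle 1 that delays administration of Cycle 2 by more than 7 days". A colon and nine bullets follow. Several bullets set narrower conditions than the general rule, for example "Grade 3 febrile neutropenia lasting > 24 hours" and "Grade 3 infusion-related reactions that recur despite appropriate medical management". The last bullet is a catch-all for other treatment-related non-hematological AEs of Grade 3 or higher, "except hyperlipidemia in subjects not receiving maximum medical management or electrolyte abnormalities that may be managed with supplements".

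**Use.** Under Section 5.2, DLTs drive changes in the L-NMMA dose, and a subject is treated past 3 weeks only if there was no DLT and no progression. Section 3.1 uses DLT status to decide who is evaluable. Section 8.0 uses it in the CRM, the early-stopping rule and the MTD.

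**The concern.** The same event can be a DLT under one sentence and not under the next, so two investigators who both follow the text could enter different counts for one cohort. The MTD is the primary endpoint and rests on at most 12 subjects in cohorts of 2. A single disputed classification can therefore change the next dose or decide whether the trial stops. It can also change whether that subject goes on to Cycle 2.

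**Working it through.** **Step 1: the two rules side by side.** Each event is assumed to occur in Cycle 1, with no clear alternative cause and no Cycle 2 delay of more than 7 days.

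| Event | General rule | Section 8.0 list |
|---|---|---|
| Grade 4 neutropenia lasting under 7 days | DLT | not a DLT |
| Grade 3 febrile neutropenia of 24 hours or less | DLT | not a DLT |
| Grade 3 thrombocytopenia, no significant bleeding, resolved within 7 days | DLT | not a DLT |
| Grade 3 electrolyte abnormality: under 72 hours, not clinically significant, managed with supplements | DLT | not a DLT |
| Grade 3 or higher hyperlipidemia without maximum medical management | DLT | not a DLT (excepted) |
| Electrolyte abnormality of 72 hours or more, managed with supplements | DLT | own bullet counts it; catch-all excepts it |
| Single Grade 3 infusion reaction | DLT | unclear: specific bullet requires recurrence; catch-all may still count it |
| Isolated Grade 3–4 ALT or AST rise | DLT | unclear: specific bullet requires a bilirubin rise; catch-all may still count it |
| Most other treatment-related Grade 3 or higher non-hematological AEs | DLT | DLT (catch-all) |

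The causality wording also differs. The general rule counts an event unless it is clearly not caused by treatment. The liver bullet asks for at least a possible relation, and the catch-all asks for treatment-related.

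**Step 2: inputs for the CRM, from Section 8.0.** L-NMMA levels are −1, 0 and 1 (12.5, 15.0 and 20.0 mg/kg). The trial starts at level 0 with cohorts of 2 and a maximum of 12 subjects. The target is 0.25 to 0.30, and α ~ N(0, variance 2). The three probability sets are (0.05, 0.10, 0.15), (0.15, 0.275, 0.40) and (0.40, 0.50, 0.60). The trial stops if Pr(toxicity at level −1 > 0.25 | data) > 0.80.

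Assumptions: equal prior weight on the three sets, and the power model π_i = p_i^exp(α), because the product as printed can exceed 1.

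For each set the likelihood is ∏ π_i^(y_i) (1 − π_i)^(n_i − y_i). Posterior means are averaged over the sets, with weights proportional to each set's marginal likelihood. The next dose is the level whose mean is closest to the target.

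**Step 3: reproduce Table 9.** Exact enumeration at target 0.25:

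| Probability of selecting no dose | Sc. 1 | Sc. 2 | Sc. 3 | Sc. 4 | Sc. 5 |
|---|---|---|---|---|---|
| Table 9 | 0.03 | 0.10 | 0.20 | 0.29 | 0.75 |
| Enumeration | 0.029 | 0.096 | 0.201 | 0.307 | 0.766 |

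All agree within 0.02, and mean numbers treated agree within 0.1. The percentages selected agree less well (largest gap 0.08; Scenario 1, level 1: 0.82 against 0.77), so I do not use them.

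**Step 4: first cohort of 2 at 15.0 mg/kg.**

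| DLTs | Posterior toxicity at −1, 0, 1 | Stopping probability | Next step |
|---|---|---|---|
| 0/2 | 0.084, 0.126, 0.173 | 0.118 | 20.0 mg/kg |
| 1/2 | 0.390, 0.480, 0.561 | 0.663 | 12.5 mg/kg |
| 2/2 | 0.658, 0.726, 0.781 | 0.944 > 0.80 | stop |

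After 0/2 the value closest to 0.25 is 0.173 (distance 0.077), and after 1/2 it is 0.390 (distance 0.140). At target 0.30 the same levels are closest (distances 0.127 and 0.090), so the assignments do not change.

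**Step 5: sensitivity.** Let f be the share of general-rule DLTs that the list would not count. The documents do not give f; I assume 0 to 0.40. The rate under the list is (1 − f) × the rate under the general rule. At f = 0.40, Scenario 5 becomes 0.6 × (0.40, 0.50, 0.60) = (0.24, 0.30, 0.36).

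| f | 0 | 0.10 | 0.20 | 0.30 | 0.40 |
|---|---|---|---|---|---|
| Scenario 5, probability of no dose | 0.77 | 0.68 | 0.57 | 0.46 | 0.35 |
| Scenario 3, mean number treated at 20.0 mg/kg | 3.5 | 4.1 | 4.7 | 5.3 | 6.0 |

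**The case against.** The best defense is that the words introducing the list make it additive, so the general rule governs. That does not remove the conflict. Nearly every bullet is already Grade 3 or higher, so the duration and bleeding limits and the exception clause would then have no effect. The list would add only the Cycle 2 delay and lower-grade hematological toxicity beyond 7 days.

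Other points narrow the matter, and they stand:

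- **Breadth.** A reader might infer that the definition fails for toxicity in general. It does not. The catch-all makes most treatment-related non-hematological events DLTs either way, including Grade 3 hypertension, and a transient blood pressure rise is the main L-NMMA effect described in Section 1.1.5.
- **Colon.** Attached to the Cycle 2 delay sentence, the list could be read as examples of delay. Section 3.1 largely settles that the bullets are DLTs in their own right.
- **Causality.** Section 7.2 records relationship as a reasonable possibility, yes or no. That brings the two bullet wordings together, and the remaining gap from the general rule is narrow.
- **Infusion reactions.** Section 5.2.1.2 permanently discontinues pembrolizumab for "Grade 3 or 4 infusion-related reactions", so a reader might infer that the recurrence bullet can never be met. That holds at most for pembrolizumab. L-NMMA is infused on five days of each cycle, so a reaction to it can recur within Cycle 1.
- **Size.** A reader might take the fall in selection of 20.0 mg/kg from 0.77 to 0.46 between Scenarios 1 and 2 of Table 9 as the effect of the ambiguity. Those are two different true toxicity curves and do not measure it. The background data also suggest that discordant events may be uncommon: Section 1.1.2.1 gives Grade 3–4 treatment-related AEs of all types in 11% to 14% of pembrolizumab subjects in one trial, and Section 1.1.5 reports no hematological abnormality with L-NMMA in a study with 3 subjects per cohort.

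**Conclusion.** The point holds in limited form: the DLT rule contradicts itself for a definable group of events, mainly hematological, electrolyte and hyperlipidemia events. Single infusion reactions and isolated transaminase rises are unclear, and the list conflicts with itself on electrolytes. It must be corrected because the primary endpoint cannot be scored reproducibly as written.

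The firmest measure of size is the first-cohort result. One reclassified event can move the next cohort from 20.0 to 12.5 mg/kg, or turn continuation into a stop. This rests on the power model and equal model weights, which are supported by the close match to the no-dose column of Table 9.

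The Scenario 5 range (0.68 to 0.35, against 0.77) illustrates an assumed 10% to 40% of uncounted events and is not an estimate; the true share could be near zero. Nor does it show that either count is wrong. The documents do not settle which rule was intended, and this review does not choose between them.

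**What to change.** Reconcile Sections 3.1 and 8.0 into one operative DLT definition, with the sponsor choosing the clinical thresholds. The amended text should:

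1. state whether the listed conditions limit the general rule, and whether the catch-all yields to a specific bullet (infusion reactions, ALT/AST);
2. keep treatment-related death, which is not among the bullets;
3. make the Cycle 2 delay a separate item;
4. use one causality standard throughout, consistent with Section 7.2;
5. resolve the electrolyte conflict between the 72-hour bullet and the supplement exception;
6. reconcile the infusion-reaction item with Section 5.2.1.2.

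Any DLT already classified should be re-adjudicated under the single rule and the CRM recommendation rerun. State that the toxicity rates in Table 9 refer to that rule. The cost is an amendment to the wording of two sections, a cross-check against 5.2.1.2, and the re-adjudication. The sample size and the CRM need not change.
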